7.4 Criteria for withdrawal / discontinuation of participants

(ClinO, Art 9; ICH/E6 6.5.3; SPIRIT #21b)

Subject withdrawal criteria (i.e., terminating investigational product treatment/trial treatment) and procedures specifying: a) When and how to withdraw subjects from the trial/ investigational product treatment. c) Whether and how subjects are to be replaced.

If a subject will be withdrawn (e. g. withdrawal of informed consent, non-compliance, disease progression, safety etc. or study or routine procedure must be stopped, e. g. due to safety concerns), a final assessment of the ear and ear canal will be carried out and all products as well as all study material that had been used have to be returned by the participant to the study site. The participants participate on a voluntary basis and can abort the participation on the study at any point of the study. The withdrawn participant will be replaced by another voluntary participant, if needed. The measurement results of the withdrawn participants will be excluded of the evaluation if the results are not complete to be included in the analysis. A new participant has to pass each study trial from the beginning.

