5.3 Other Outcomes of Interest

Other outcomes of interest are potential side effects and informal feedback from the subjects regarding subjective rating of the performance. Additionally further measures (e.g. regarding psychoacoustic function) may be used to determine the individual hearing abilities and/or compare and correlate these results with the ones from the primary outcomes (Table 6Table 6:).

Table 6: Additional further measures

Performance	Aim	Method	Result [unit]
Auditory function	Assess Psychoacoustic measures	Basic psychoacoustic measurements (e.g. ITD/IPD/ILD, JNDs, BMLDs, frequency discrimination thresholds, measures of frequency selectivity, frequency modulation detection), Tinnitus pitch and loudness matching, TEN (Threshold-Equalizing-Noise) Test [48 - 51]	Detection threshold
Behavioural observations	Observation of behaviour during the test session	Video analysis, recordings, motion- and position sensor, reaction time measurement	Analysis of respective observation method
Peripheral psychophysiological observations	Assess Peripheral psychophysiological measures	HEG (hemoencephalography), EEG (electroencephalography), ECG (electrocardiogram), EMG (electromyography), EDA (Electro Dermal Activity or Galvanic Skin Response), Respiratory rate, Pulse rate, Pupillometry [52 – 54]	Respective result of peripheral psychophysiological measure

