8.5 Data Collection and Follow-up for withdrawn participants

(ICH/E6 6.5.3; AGEK 9.2; SPIRIT #18b)

ICH:b) The type and timing of the data to be collected for withdrawn subjects. d) The follow-up for subjects withdrawn from investigational product treatment/trial treatment.

The subjects participate on a voluntary basis and can abort the participation on the study at any point of the study. The withdrawn subject will be replaced by another voluntary subject. The measurement results of the withdrawn subject will be included to the evaluation if data are complete for the appropriate trial. The new subject has to pass each study trial from the beginning.

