9.2.3 Assessment of other outcomes of interest

ICH: Methods and timing for assessing, recording, and analysing of efficacy & safety parameters.

Other outcomes of interest like side-effects will be carefully investigated, evaluated and documented. This outcome will also be documented in the form of questionnaires. Additional further measurements (investigating basic psychoacoustic function for instance) will be done at specifically defined study appointments if necessary (Reference to section 5.3 Other Outcomes of Interest).

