11.4.5 Safety analysis

The safety analysis will be done permanently during the study by the PI.

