11.5 Handling of missing data and drop-outs

(ICH/E6 6.9.5; AGEK 8.5; SPIRIT 20c)

ICH: Procedure for accounting for missing, unused, and spurious data.

If data records are complete from subjects who dropped out of the study early, these data will also be used in the analysis. If the data sets are not complete, they will not be integrated in the analysis.

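### Section 11.5 excludes incomplete data sets with no exception for side effects, and no safety set is defined, so participants who stop because of a side effect can be lost from the side-effect summary

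*Combined protocol and SAP*

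**What the plan says.** **Side effects as an outcome.** Section 5.3 states: "Other outcomes of interest are potential side effects and informal feedback from the subjects". Section 9.2.3 says they will be investigated and evaluated, and adds: "This outcome will also be documented in the form of questionnaires". Section 10.3.1 asks participants to note unexpected incidents in the questionnaires. Safety objectives (4.4) and safety outcomes (5.4) are marked not applicable, so section 5.3 is where side effects enter as an outcome.

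**Withdrawn participants.** Four sections deal with their data:
- Section 7.4, which lists safety as a withdrawal reason: "The measurement results of the withdrawn participants will be excluded of the evaluation if the results are not complete". Replacement is conditional on need.
- Section 8.5: "The measurement results of the withdrawn subject will be included to the evaluation if data are complete for the appropriate trial". Replacement here is unconditional: "The withdrawn subject will be replaced by another voluntary subject".
- Section 11.4.1 opens by including all participants in the analysis. It then leaves it to the statistician whether a withdrawn participant's data are used in part or dropped altogether. Under section 1.3 the statistician is the principal investigator.
- Section 11.5: "If the data sets are not complete, they will not be integrated in the analysis".

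**Safety analysis.** Section 11.4.5 is a single sentence: "The safety analysis will be done permanently during the study by the PI". It names no population, denominator or summary.

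**The concern.** For hearing performance, a completers-only rule costs precision and may cost some validity. For side effects it is worse, because the side effect can itself be the reason the record is incomplete. Section 3.7 lists pressure points, tinnitus and headache as known risks and describes leaving the device off or interrupting its use when they occur. Section 10.3.1 tells participants not to wear a device that becomes uncomfortable or painful. Someone who stops in the middle of a home trial for such a reason is incomplete for that trial, even under the more lenient wording of section 8.5.

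If the general rule in section 11.5 is followed to the letter, that person's side-effect entries leave the summary. The remaining participants are more likely to be those who tolerated the setting, and the reported rate is too low. Replacement then brings the count back to target, so a reader of the report cannot see from the denominator that anyone is missing. What is at stake is whether a setting that makes people stop is described fairly next to its comparator.

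**Working it through.** **1. What the documents supply.** There is no side-effect rate, withdrawal rate or planned side-effect comparison, so there is no figure of the plan's own to reproduce on this point. The only usable number is the size of a main study, 20 to 25 participants (11.2). The rates below are assumptions, shown as a range.

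**2. Formula.** Let p be the true share of participants with a side effect. Let f be the share of those affected who stop with incomplete data and are excluded. Assume everyone else completes, and that withdrawn participants are replaced until N are complete.
- Share of starters who complete: 1 − pf.
- Reported rate among completers: p(1 − f) / (1 − pf).
- Expected number started: N / (1 − pf).

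The reported rate does not depend on N, so the exclusion alone creates the bias. Replacement only restores the count.

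**3. Varying f at p = 10%.**

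| f | Reported rate |
|---|---|
| 0% | 10.0% |
| 25% | 0.075 / 0.975 = 7.7% |
| 50% | 0.050 / 0.950 = 5.3% |
| 75% | 0.025 / 0.925 = 2.7% |
| 100% | 0% |

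**4. Varying p at f = 50%.**

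| p | Reported rate | Share of true rate |
|---|---|---|
| 5% | 0.025 / 0.975 = 2.6% | 51% |
| 10% | 0.050 / 0.950 = 5.3% | 53% |
| 20% | 0.100 / 0.900 = 11.1% | 56% |
| 30% | 0.150 / 0.850 = 17.6% | 59% |

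**5. Chance of reporting no case at all**, with N = 20, p = 10% and f = 50%:
- Under exclusion: (1 − 0.0526)^20 = 34%.
- If everyone who started counts: (1 − 0.10)^20 = 12%.

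**6. Extreme case.** Twenty completers have no side effect, two participants withdraw for one, and both of their records are discarded. The report shows 0/20. Counting all who were exposed gives 2/22 = 9.1% (exact 95% CI 1.1% to 29.2%).

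**7. When the bias vanishes.** It is zero if f = 0, or if the adverse-event records of withdrawn participants stay in the count. Whether they stay is what the plan leaves open.

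**The case against.** The strongest reply is that no sentence applies the completeness rule to side effects. Sections 7.4 and 8.5 speak only of measurement results, and the protocol keeps measurements apart from adverse events. The visit schedules give capture of adverse events and device deficiencies its own row, and section 12.1.2 lists them as separate source data. Section 9.2.4.1 has problems reported at once, asked about after each home trial and entered in the eCRF. Section 9.2.5 sets out follow-up after withdrawal with an adverse event, and section 10.3.2 provides an adverse-event eCRF. The safety analysis runs throughout the study, so it need not wait for a completers' data set. Section 11.4.1 starts from all participants and permits partial use.

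Most of this stands, and it rules out stronger readings that a reader might infer:
- *That side-effect data of withdrawn participants are certain to be lost.* The documents do not say so. The inference rests on the general wording of section 11.5 and the discretion in 11.4.1.
- *That withdrawn participants are replaced by people who tolerate the device.* Replacements are simply other volunteers. Any selection comes from the requirement to finish.
- *That a setting would be reported as free of side effects.* That needs every affected participant to withdraw, no completer to report anything, and all withdrawn records to be discarded.

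The separate track does not close the gap. It covers capture, care and reporting of events. It does not say whose events are summarised in the results, or over what denominator. The adverse-event eCRF in section 10.3.2 is prescribed for unexpected events, whereas tinnitus, headache and pressure points are listed as known risks. Section 9.2.4.1 means the information should exist, but it does not bring that information into the analysis.

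**Conclusion.** The point holds as a possible, not a certain, loss. The plan's only missing-data rule has no exception for side effects, the analysis-set section allows complete removal of a withdrawn participant at the discretion of the principal investigator acting as statistician, and no safety set is defined. A literal application removes from the side-effect summary those who stopped because of a side effect, and the resulting bias is downward.

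Its size cannot be fixed from the documents. Under the assumption that half of those affected stop and are excluded, the reported rate is roughly 51% to 59% of the true rate for true rates of 5% to 30%. The contrast of 0/20 with 2/22 is a boundary case and should not be read as the expected result.

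**What to change.** Add to sections 11.4.5 and 11.5 wording along these lines: *Side effects, adverse events and device deficiencies are summarised for every participant fitted with any study device, including withdrawn and replaced participants, whether or not the record is complete. Results are shown by the device or setting in use, with pre-study participants shown separately. The completeness rule applies to performance measurements only.* Withdrawals for side effects should be listed by the device or setting in use.

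Sections 7.4, 8.5, 11.4.1 and 11.5 should then be reconciled. They need to agree on what counts as complete, on whether replacement is conditional, and on how far the statistician's discretion reaches. Each should refer to the side-effect rule.

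The cost is a few sentences and slightly more reporting work. The data are already to be collected, and no visit, participant or clinical procedure changes. Reported side-effect rates may look less favourable.

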1.3 Statistician ("Bios tatis tician")

(ICH/E6 6.1.7; SPIRIT 5a-d)

ICH: Name(s) and address(es) of the clinical laboratory(ies) and other medical and/or technical department(s) and/or institutions involved in the trial.

The role as the Statistician is adopted by the Principle Investigator.

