6.2.1 Randomization

As this is a controlled cross-over study each subject serves as his or her own control. For the reduction of order effects the sequence of the tested settings (and/or tested devices) will be randomized. To do so block randomization will be used. The randomization is applied to all investigational settings for both the laboratory trials and the trials in real world environment. For sub-studies with several test methods the order of the test methods will be also randomized with help of block randomization. Randomization and concealment of randomization list is generated by the Principle Investigator. For laboratory tests where several individual ratings are executed with help of computer controlled testing procedures (e.g. software tool for MUSHRA test) simple randomization is applied to the sequence of the respective settings. This simple randomization is done automatically by the tool, the individual simple randomization can be examined afterwards.

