11.4.1 Datasets to be analysed, analysis populations

ICH: The selection of subjects to be included in the analyses (e.g., all randomized subjects, all dosed subjects, all eligible subjects, evaluable subjects).

The data of all participants and measurement methods will be analysed. Subgroups typically composed are hearing loss dependent groups (mild, moderate, severe, profound) and groups depending on their experience level wearing hearing instruments or using accessories (non-experienced, short-term, experienced, long-term user). In case of a subject withdrawal, the statistician will decide if the data can be used for a part of the statistical analysis or if the data will be dropped out completely.

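### A participant who leaves because a setting stays intolerable is not counted against that setting, so comfort and preference results can tilt towards it

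*Combined protocol and SAP*

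**What the plan says.** Four sections govern the data of someone who leaves.

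- Section 7.4: the measurement results "will be excluded of the evaluation if the results are not complete to be included in the analysis". Replacement is made if needed.
- Section 8.5: the results "will be included to the evaluation if data are complete for the appropriate trial". On replacement: "The withdrawn subject will be replaced by another voluntary subject".
- Section 11.5: complete records of early drop-outs are used. Otherwise, "If the data sets are not complete, they will not be integrated in the analysis".
- Section 11.4.1: "The data of all participants and measurement methods will be analysed". After a withdrawal, however, "the statistician will decide if the data can be used for a part of the statistical analysis", the alternative being to discard them altogether. No criterion is given.

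Section 1.3 says who decides: "The role as the Statistician is adopted by the Principle Investigator". Section 6.2.1 adds: "Randomization and concealment of randomization list is generated by the Principle Investigator". Nothing requires the use-or-discard decision to be made without knowledge of setting or results.

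Section 10.3.1 foresees a setting that a participant cannot accept or tolerate. The person is to stop wearing the device and ask for an additional appointment. If the setting is still intolerable after that, the plan does not say how the outcome is to be scored. Section 9.2.5 plans an audiogram and ear check, or a medical referral after an adverse event. It does not ask for the setting in use or the reason for stopping. Section 11 has no table of stops by setting and no sensitivity analysis for them.

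**The concern.** Sound quality / hearing comfort is one of the three primary performance dimensions (5.1, Table 4), measured among other ways by paired preference and rating scales. On that dimension, giving up a setting as intolerable is itself a bad result for the setting. The exclusion rules make no distinction by cause, so this result is treated like a missed visit. Those who remain are the people who could tolerate the setting, and a comparison among them alone favours it.

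Replacement restores the number of participants but not the lost result, and it makes the loss harder to see. With 20 to 25 people per main study, one or two such losses can move a reported preference by several points. The protocol covers a ten-year series of sub-studies, so the same gap recurs in each.

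**Working it through.** **Reproducing the plan's figure.** Section 11.2 gives 20–25 participants per main study. This cannot be rebuilt, because no effect size, standard deviation, power or drop-out rate is stated. It serves below only as the scale of a study. All stop rates are assumed.

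**Preference: formula.** Let q be the share of completers preferring the novel setting, and rn and rc the shares of starters who stop because of the novel setting or the comparator.

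- Result among completers: q.
- Result with each such stop counted as unfavourable to its setting: q × (1 − rn − rc) + rc.
- Tilt (the difference): q × rn − (1 − q) × rc.

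**Tilt in percentage points.** A positive value overstates the novel setting.

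| q | rn | rc | Tilt |
|---|---|---|---|
| 75% | 2% | 0 | +1.5 |
| 75% | 5% | 0 | +3.75 |
| 75% | 10% | 0 | +7.5 |
| 75% | 20% | 0 | +15.0 |
| 75% | 0 | 5% | −1.25 |
| 75% | 0 | 10% | −2.5 |
| 75% | 0 | 20% | −5.0 |
| 75% | 5% | 5% | +2.5 |
| 60% | 10% | 0 | +6.0 |
| 85% | 10% | 0 | +8.5 |

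**As counts.** The completers' result is 15/20 = 75.0%.

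- One novel-setting stop: 15/21 = 71.4%.
- Two novel-setting stops: 15/22 = 68.2%. Check: rn = 2/22 = 9.1%, and 0.75 × 9.1 = 6.8 points = 75.0 − 68.2.
- Two comparator stops: (15 + 2)/22 = 77.3%.

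**Does replacement matter?** With q = 75% and rn = 10%, reaching 20 completers takes 20/0.90 = 22.2 starters on average. Completers still show 75.0%, and all starters show 0.75 × 0.90 = 67.5%. Without replacement the two percentages are the same. Exclusion causes the tilt, and replacement leaves it unchanged.

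**Comfort ratings.** Suppose there is no true difference, the paired difference has standard deviation 1, and the least tolerant share r leaves on a tolerability score correlated ρ with that difference. The shift among completers is ρ times its value at ρ = 1, which a simulation puts at about 0.195 SD for r = 10% and 0.350 SD for r = 20%.

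- ρ = 0: no shift.
- ρ = 0.5, r = 10%: 0.5 × 0.195 = 0.10 SD.
- ρ = 0.7, r = 10%: 0.7 × 0.195 = 0.14 SD.
- ρ = 0.7, r = 20%: 0.7 × 0.350 = 0.24 SD (0.245 before rounding; simulated 0.244).

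The shift needs a link between leaving and dislike of the setting.

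**How likely is one such stop?** For 20 independent starters the chance of at least one is 1 − (1 − r)^20: 18% at r = 1%, 33% at 2% and 64% at 5%.

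**The case against.** **The path is narrow.** Output is limited and loud sounds are tolerance-tested (8.6), the pre-study screens settings, and fine tuning is allowed (9.3.2). Section 3.7 has participants with headache pause use until refitted, and 10.3.2 foresees interruption as well as cancellation after an unexpected adverse event. A loss needs a setting that stays intolerable after all this and a person who leaves before the trial part is complete. Those who dislike a setting but stay still rate it. This stands, and it makes stops rarer. It does not say how a remaining stop is scored.

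**The rules can largely be read together.** Read with 8.5, completed parts are kept and unfinished parts dropped. This also stands. A reader might infer that the plan discards everything from anyone who leaves, but 8.5 and 11.5 say otherwise. The real conflict is with the option in 11.4.1 to discard a leaver's data entirely, complete parts included.

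**Stops leave a trace.** Problems go into the eCRF (9.2.4.1), side effects are documented (9.2.3), and the final report covers all phases (12.1). A reader might infer that stops are hidden, which would be too strong. What is missing is the link to a setting and to the comparison.

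**Preference among people who tolerate both settings is a legitimate quantity.** Section 11.1 tests no specific hypothesis. This is a good reason to put the alternative scoring in a sensitivity analysis and leave the main one alone. But the plan does not declare this restricted target, and 5.1 intends conclusions about superiority.

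**The discretion in 11.4.1.** A reader might infer a measurable inflation of the false-positive rate from choosing whichever option gives the smaller p-value. The documents do not support a figure. A leaver can enter a paired test only with both settings measured, and 8.5 and 11.5 already direct such data into the analysis. Someone without a pair cannot enter it under either option. The Principal Investigator's several roles are a separate matter. They count here only because the decision has neither a criterion nor blinding.

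**Conclusion.** The point holds within limits. The plan excludes a leaver's incomplete data whatever the cause, allows complete data to be discarded without a criterion, and neither counts nor tabulates a setting-related stop against the setting. Comfort and preference results can therefore tilt towards an abandoned setting.

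On assumed rates of 2% to 20% for stops due to the novel setting, and 75% of completers preferring it, the tilt is 1.5 to 15 points. The true rate is unknown and may be zero, in which case there is no effect. These figures count each setting-related stop as unfavourable to that setting.

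Two stronger readings are not supported. One is that the plan favours the novel device: the mechanism is symmetric, and comparator stops understate the novel setting. The other is that the primary laboratory results are generally compromised: 8.5 keeps data complete for the trial concerned. Exposure is mainly in home-trial outcomes, which are secondary and, under 11.2, mainly descriptive. This is an inexpensive improvement to analysis and reporting.

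**What to change.** 1. Replace the discretion in 11.4.1 and the exclusion in 7.4, 8.5 and 11.5 with one rule, fixed in advance: use all available data of everyone who started, including those later replaced, as far as consent allows.
2. In 9.2.5, record the setting in use and the reason for the stop at the final appointment already planned.
3. In section 11, report setting-related stops per setting. Add one sensitivity analysis for comfort and preference outcomes that counts such a stop as unfavourable to that setting, novel or comparator alike.

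Item 1 alone is not enough, because a person who never completed one setting has no pair to contribute. Item 3 covers that case.

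The cost is protocol wording, two recorded items, one table and one extra analysis, with no new participants or visits. The downside is a little more analysis work and a possibly less favourable reported benefit.
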